10.0 SERIAL MEASUREMENTS (see Table 1 in Section 6.3)

- 10.1 Time of entry into the study: ^{99m}Tc bone scan, X-rays and/or CT or MRI evaluation of the primary and metastatic lesions (specific modality at clinician's discretion). A pre-treatment [^{18}F]-MISO/ [^{18}F]-FDG PET scan will be obtained for baseline readings as part of study.
- 10.2 One month after completion of external beam radiotherapy: repeat initial imaging modality and territories, as well as any other imaging clinically indicated. [^{18}F]-MISO/ [^{18}F]-FDG PET will be obtained at that time as well.
- 10.3 Subsequent follow up as per Table 1. Scans will be repeated every 4 months for the first year after completion of therapy, every 6 months during the second year after therapy, and yearly thereafter for a total of 5 years.
- 10.4 At progression, patient will undergo repeat [^{18}F]-MISO/[^{18}F]-FDG PET.

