5.4 REGISTRATION

To register a patient, the following documents should be completed by the Research Nurse or Study Coordinator and faxed [contact]) or emailed ([contact]) to the Coordinating Center:

- Fax cover sheet
- Registration form
- Signed patient consent form
- HIPAA authorization form
- Eligibility screening checklist

Copy of required screening tests and scans The Coordinating Center will then verify eligibility and complete the registration process, by:

- Assigning a patient study number
- Registering the patient on the treatment portion of the study with the Sidney Kimmel Comprehensive Cancer Center's Clinical Research Office
- Faxing or e-mailing the patient study number to the participating site
- Calling or e-mailing the research nurse or data manager at the participating site, verbally confirming registration and the last eligible start date for treatment.

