The first portion of the combined plan, that is, the second, “treatment” ^{153}Sm -EDTMP infusion, will then be implemented on Day 8. Maximum activity administered will be 30 mCi/kg, which is the maximally tolerated dose permitting recovery of myelosuppression with auto-stem cell infusion (14). After the “treatment” infusion, SPECT scans will again be performed to confirm total dose delivered and subsequently adjust the external beam portion of the treatment plan, as necessary. External beam radiotherapy will begin as early as possible between Days 15 and 22. The total dose to be used will be modified based on surrounding tissue tolerances. On Day 24, previously harvested autologous peripheral blood or bone marrow stem cells will be infused in order to ameliorate the expected myelosuppression. External beam radiation therapy will not be administered on Day 24 (anticipated to be a Friday), nor on Days 25 or 26, in order to provide time for infused hematopoietic stem cells to home to the bone marrow and leave the circulation.

Patients will be reimaged one month following completion of external beam radiation by CT/MRI for evidence of clinical response (defined as stable disease or better by RECIST 1.1 criteria) or disease progression. In the event of progression of a single lesion, local therapy such as radiofrequency ablation or cryoablation may be provided so that the response of stabilized lesions can continue to be monitored. If suspicious lesions remain on

thoracic CT scan or on MRI of the primary site after the completion of therapy, further evaluation by biopsy may be clinically indicated, and potentially surgical intervention pursued if persistent disease is found. Percent necrosis of any resected tumor will be evaluated pathologically.

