6.3 ON-STUDY EVALUATION

- 6.3.1 Dosimetric studies by ^{153}Sm SPECT/CT to be assessed at approximately 4, 24, and 48 hours after injection of tracer dose of ^{153}Sm -EDTMP; SPECT/CT will also be collected at approximately 4, 24, and 48 hours following the therapeutic administration of ^{153}Sm -EDTMP. Scans can be obtained at any time on the first and second day after infusion of ^{153}Sm -EDTMP, as long as the specific number of hours post-infusion is recorded.
- 6.3.2 Complete evaluation, including history and physical exam, vital signs, weights, and laboratory evaluation including complete blood counts and a complete metabolic panel, Mg and Phosphorous to be performed weekly until hematopoietic recovery and until recovery from therapy-related toxicities.
- 6.3.3 Because of the risk of renal and bladder toxicity from the excretion of ^{153}Sm -EDTMP that is not adsorbed to tumor, care will be taken to monitor patients closely for urinary tract toxicity. Prior to treatment, patients will have a complete urinalysis, measurement of BUN and creatinine, and 24- hour urine collection for creatinine clearance. These tests will be repeated as clinically indicated based on urinary symptoms and at the completion of therapy.
- 6.3.4 Restaging evaluation to include radiologic imaging by CT or MRI of the primary tumor and metastases, follow up [^{18}F]-MISO/[^{18}F]-FDG PET, plain radiographs of primary lesion, and Tc-99m bone scan. These studies will occur approximately one month after completion of external beam radiotherapy. Based on our prior experience with [^{18}F]-FDG PET and the lack of correlation between clinical response and SUV levels, we will not use [^{18}F]-MISO/[^{18}F]-FDG PET SUVmax measurements to determine clinical response while the patient is receiving treatment.

- 6.3.5 CT scan of chest and Tc-99m bone scan every 4 months after completion of therapy for one year, then every 6 months for 1 year, and then yearly for 3 years. Thereafter scans will be repeated only as clinically indicated.
- 6.3.6 Evaluation for long-term skeletal toxicity will be performed every 6 months for the first 4 years after completion of therapy, and will include alkaline phosphatase and LDH (bone fractions), serum C-telopeptide and parathyroid hormone levels, and bone density scans.
- 6.3.7 If any lesions are resected after patient has completed radiation therapy, percent necrosis will be determined by the pathologist and recorded.

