6.4 Schedule of Assessments

Table 1. Schedule for On-Study Patient Evaluations.

(Note this does not include additional clinically appropriate testing in the setting of stem cell rescue and routine monitoring while on external beam radiation therapy.)

Evaluation	PreTx ¹	1 st Sm	2 nd Sm	External Beam Radiation				
	Week	1	2	3	4	5	>	
1 st Day of Week	-3- 0	1	8	15	22	24	29	
H&P, Vital signs and Wt	x	x	x	X ³	x		x	
Ht and BSA (baseline only)	x							
CBC	x		x	x ³	x		x	
CMP	x		x	x ³	x		x	
Ca/Phosphorus/Mg	x		x	x	x		x	
Alk Phos ⁴ , LDH ⁴	x							
C-telopeptides (JHH Path test code 6315) + PTH	x							
Ionized Ca level ⁵		x	x					
Urinalysis	x							
Creatinine Clearance ⁶	x							
Hematopoietic stem cell (HSC) collection ⁷	x							
EKG ⁸	x	x	x					
Chest X-ray	x							
CaCO ₃ (oral)		X ⁹	X ⁹					
Mycotic disease prophylaxis ¹⁰ (oral)		x	x	x	x	x	x	
Pneumocystis carinii pneumonia prophylaxis ¹¹ (oral)		x	x	x	x	x	x	
Stem Cell Infusion						x		
Rad Onc Planning CT	x ¹²							
¹⁵³ Sm planar imaging of abdomen			x ¹³					
SPECT/CT		X ¹⁴	X ¹⁴					
CT/MRI ¹⁵	x							
CT chest								
^{99m} Tc-Bone Scan	x							
Plain radiographs of primary lesion	no							
¹⁸ F-FDG PET/CT	x							
¹⁸ F-MISO PET	x							

- Table 1 Footnotes: ¹ Pre-treatment radiographic evaluation must be obtained within 3 weeks of study entry. Pre-treatment laboratory studies must be obtained within 2 weeks of study entry. Blood tests need not be repeated prior to first ¹⁵³Sm-EDTMP treatment.
- ² Start between D15 and D22
- ³ Weekly H&P, labs til CBC and AE recovery
- ⁴ Alk phosphatase and LDH will be fractionated if elevated. (Quest lab referral tests)
- ⁵ Check prior to administration of ¹⁵³Sm-EDTMP
- ⁶ Measured creatinine clearance or nuclear medicine GFR. Do not use calculated creatinine clearance.
- ⁷ Ifos + Mesna x 5 days recommended. Peripheral CD-34 cell count done daily starting at chemo D7 until high enough for pheresis.
- ⁸ Obtain at screening, pre and at completion of ¹⁵³Sm-EDTMP infusions on Days 1 and 8.
- ⁹ CaCO₃ to be administered prior to ¹⁵³Sm-EDTMP; 1000 mg calcium carbonate the morning of each samarium infusion
- ¹⁰ Days 1-75
- ¹¹ From Day 1 until 6 months after completion of therapy
- ¹² Timing of Rad Onc Planning CT relative to study entry at discretion of treating physician, and coordinated by Radiation Oncology.
- ¹³ ¹⁵³Sm planar imaging of the abdomen will be performed at 1 and 2 hours after the “treatment” infusion.

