- ¹⁴ SPECT/CT scans to be obtained after ¹⁵³Sm-EDTMP infusions at approximately 4, 24, and 48 hrs post each injection of ¹⁵³Sm-EDTMP. The 24 and 48 hour post- infusion SPECT/CT scans can be obtained any time one and two days after treatment, as long as the specific number of hours post-infusion is recorded.
- ¹⁵ Choice of imaging modality and location as clinically indicated. To include primary tumor and any large metastases.
- ¹⁶ Four tubes of venous blood drawn 5 minutes apart; drawn only in conjunction with FMISO PET scans, and are to be processed by nuclear medicine as a part of that scan protocol.

Table 2. Schedule for Post Treatment and Follow Up Patient Evaluations

Evaluation	Post Tx Assessment (30 days after final tx)	Months post End				
		4	6	8	12	18
H&P, Vital signs and Wt	X	X	X	X	X	X
CBC ¹	X	X	X	X	X	X
CMP ¹	X	X	X	X	X	X
Phosphorus, Mg	X	X	X	X	X	X
Alk Phos ² , LDH ²	X		X		X	X
C-telopeptides (JHH Path test code 6315)	X		X		X	X
PTH	X		X		X	X
Bone density scan			X		X	X
Urinalysis	X					
Creatinine Clearance ³	X		X		X	X
Chest X-ray		X		X	X	X
Mycotic disease prophylaxis ⁴	X (thru D75)					
Prophylaxis for Pneumocystis carinii pneumonia (PCP) ⁵	X	X	X			
CT/MRI ⁶	X	X		X	X	X
CT chest		X		X	X	X
^{99m} Tc-Bone Scan	X	X		X	X	X
Plain radiographs of primary lesion	X					
¹⁸ F-FDG PET/CT	X			X	X	
¹⁸ F-MISO PET	X			X	X	
Blood samples with F-MISO PET ⁷	X			X	X	

¹ly H&P, labs til CBC and AE recovery

² Alk phosphatase and LDH will be fractionated if elevated. (Quest lab referral tests)

³ Measured or nuclear medicine GFR

⁴ Days 1-75

⁵ From Day 1 until 6 months after completion of therapy.

⁶ Choice of imaging modality and location as clinically indicated. To include primary tumor and any large metastases.

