Survival curves will be estimated by using the Kaplan-Meier method. Progression-free survival is defined as time from registration to the first observation (documentation) of disease progression or death. Patients who are lost to follow-up will be censored for determination of PFS on the date of their last evaluations. Overall survival is defined as time from registration to death due to any cause.

11.3.6 Determine correlation of hypoxic volume and maximum tumor/blood ratio obtained by [¹⁸F]-MISO PET scanning with patient outcomes.

Cox regression analysis will be performed to measure association between hypoxia based on HV and max T/B ratio with Kaplan-Meier survival and time-to-progression curves. Additional regression analysis will be performed to evaluate the link between hypoxic indices and uptake of ¹⁵³Sm-EDTMP and clinical response based on radiologic response and presence of necrosis on histology.

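### 6-month PFS is counted from registration but tumour scans are timed from the end of radiotherapy, with none fixed at 6 months, so the primary estimate depends partly on treatment timing

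*Combined protocol and SAP*

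**What the plan says.** Two clocks are in use.

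- **Endpoint clock.** Section 11.3.5: "Progression-free survival is defined as time from registration to the first observation (documentation) of disease progression or death". Sections 11.1 to 11.3.1 make 6-month PFS the primary endpoint for Stratum 1, estimate it by Kaplan-Meier, and use the same quantity in the futility rule.
- **Imaging clock.** Section 6.3.4 on restaging: "These studies will occur approximately one month after completion of external beam radiotherapy". Section 6.3.5 continues with "CT scan of chest and Tc-99m bone scan every 4 months after completion of therapy for one year", and section 10.3 says of scans in general: "Scans will be repeated every 4 months for the first year after completion of therapy". In section 6.4, Table 2 ("Schedule for Post Treatment and Follow Up Patient Evaluations") counts months from the end of treatment. It marks CT/MRI, chest CT and bone scan at months 4, 8, 12 and 18. Its month-6 column, also counted from the end of treatment, has none of the three.

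The time between the two origins is only partly specified. Section 6.2 says "External beam radiotherapy will begin as early as possible between Days 15 and 22". The length of the course is left open, because section 6.2.5 sets the external beam dose per patient from the samarium dosimetry. The time from registration to Day 1 is not stated.

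The documents give no visit window, no interval-censored method and no sensitivity analysis for assessment timing. The simulations in section 11.3.1 describe exponential survival and staggered entry, but no scan schedule.

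**The concern.** Progression is dated when it is documented, so a patient whose tumour has grown by month 6 counts as progression-free at month 6 unless a death, a clinical finding or a scan shows otherwise by then. The last informative scan before the landmark is either the 4-month one, close to month 6, or the 1-month one, near month 3. Which of the two it is depends on how soon treatment started and how long radiotherapy ran, not on disease activity. The error has one direction: the estimate can only read high.

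Three things follow. The reported 6-month PFS and its 95% confidence interval carry a systematic component that the interval does not show. The futility rule, fed by the same estimate, stops less often than its table says. And because the trial has one arm and is compared with a fixed 15.8%, no concurrent control shares the distortion.

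The scan date is also unclear for patients who stop before or during external beam, whom section 11.2 keeps in the PFS analysis.

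**Working it through.** **1. The plan's own figures.** Section 11.3.1 gives a null 6-month PFS of 15.8% and a benchmark of 35%. Hazards: −ln(0.158)/6 = 0.3075 and −ln(0.35)/6 = 0.1750 per month. Their ratio is 1.76 and the null median is ln 2/0.3075 = 2.25 months, as stated. A single-arm exact exponential test with 20 events, one-sided 0.05, gives 82.3% power against the stated 82%.

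**2. When the 4-month scan passes month 6.** Time from registration to that scan = lag + external beam start + course + 4 months. It falls by month 6 if external beam ends within 2 months (8.7 weeks) of registration. Day 15 to Day 22 is 2 to 3 weeks after Day 1, so the longest course that still qualifies is:

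- no lag: 8.7 − 3 to 8.7 − 2 = 5.7 to 6.7 weeks
- 1-week lag: 4.7 to 5.7 weeks
- 3-week lag: 2.7 to 3.7 weeks

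**3. Effect for one patient.** Let f be the share of the hazard seen as it occurs (deaths, progression found at visits) and L the last scheduled scan at or before month 6. Then apparent PFS = exp(−0.3075 × [6f + (1 − f)L]).

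- External beam ends at 2.0 months: L = 6.0, so the null reads 15.8%.
- External beam ends at 2.1 months: the 4-month scan is at 6.1, so L = 2.1 + 1 = 3.1. With f = 0 the null reads exp(−0.3075 × 3.1) = 38.5%, above the 35% benchmark. With f = 0.5 it reads exp(−0.3075 × 4.55) = 24.7%.

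**4. Effect averaged over patients.** Assumptions, because the documents give no figures: lag and course uniform over the ranges shown, external beam start uniform over Days 15-22. f = 0 (scan-only detection) is an upper bound. The futility simulation uses looks at 8, 12 and 16 patients, one entry per 3 months on average, the beta(1,4) prior and an effective sample size from the Greenwood variance, with 6,000 trials (Monte Carlo SE 0.006).

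| Lag; course | 4-month scans after month 6 | True 15.8% reads (f = 0.5 / f = 0) | Futility stop at true 15% (f = 0.5 / f = 0) |
|---|---|---|---|
| 0; 3-6 wk | 1.5% | 16.9% / 18.2% | 0.34 / 0.29 |
| 0-1 wk; 3-6 wk | 12% | 17.6% / 20.0% | 0.33 / 0.25 |
| 0; 4-7 wk | 27% | 18.6% / 22.9% | 0.30 / 0.19 |
| 0-3 wk; 3-6 wk | 44% | 19.9% / 25.9% | 0.27 / 0.15 |

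**5. How far to trust the futility column.** With exact progression dates the simulation gives 0.57, 0.40, 0.27 and 0.07 at true PFS 0.10, 0.15, 0.20 and 0.35. The protocol's table gives 0.60, 0.39, 0.23 and 0.04, so the simulation misses by up to 0.04. The exact-date run made alongside the table above gave 0.41 at PFS 0.15.

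**6. Scale.** The binomial standard error at N = 20 is √(0.158 × 0.842/20) = 0.082.

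**7. Re-timed scan.** With the 4-month set placed at 6 months ± 2 weeks from registration and counted at the landmark, apparent PFS is 15.7-16.1% in all four scenarios. Futility stopping is 0.35-0.37 in the two scenarios run (no lag, and 0-3 week lag). The hazard rate from documented dates is not repaired: a true 0.308 reads 0.20-0.25 either way.

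**The case against.** The larger figures need a lag that the documents make less likely. Table 1 places pre-treatment work-up in weeks −3 to 0, its first footnote says "Pre-treatment radiographic evaluation must be obtained within 3 weeks of study entry", and blood tests need not be repeated before the first infusion. These fit best if entry is close to Day 1. This stands in part: the three weeks concern imaging around entry, not a lag after it. But section 5.4 has the coordinating center "verbally confirming registration and the last eligible start date for treatment", so treatment follows registration by an unstated time and zero cannot be assumed.

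Course length is assumed too. With no lag and a 2-5 week course no 4-month scan passes month 6. The null then reads 17.4% (f = 0.5) or 19.2% (f = 0), which is ordinary scan-interval delay. That is correct, but the plan does not limit the course to that range.

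Scan-only detection is unrealistic, given frequent examinations, a month-4 chest X-ray and death as an event. Agreed: it is a bound only. With f = 0.75 and no lag the null reads 16.3-17.1%.

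The futility shift depends on the implementation, because the effective-sample-size formula is not given in detail. A separate implementation (3,000 trials) gave 0.44 with exact dates and 0.44/0.40 in the mildest case, so there the shift nearly vanishes. The harsher scenarios still move.

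If the 11 historical patients were also read by documentation date, some of the bias cancels. Their scan schedule is not given, so this can be neither shown nor excluded.

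**Conclusion.** The concern holds. The primary landmark and the imaging schedule have different origins, and nothing in the plan ties a scan to month 6. The Kaplan-Meier estimate at 6 months reads at or above the truth. With a true 15.8% the excess runs from 1-2 points in the mildest case examined (no lag, 3-6 week course) to 4-10 points in the harshest (0-3 week lag). The first is small beside the 8-point standard error; the upper end of the second exceeds it. Futility stopping at a true 15% falls from about 0.40 to somewhere between 0.34 and 0.15, and the mildest shift is barely larger than the simulation's own error.

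All sizes rest on assumed lag, course length and share of events seen between scans. The direction of any net bias against 15.8% is not established. The stated power calculation reproduces. This is a worthwhile and inexpensive improvement, not a defect that invalidates the design; confidence in the size is medium.

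**What to change.** For Stratum 1, move the imaging set now labelled 4 months post end as a whole (CT/MRI, chest CT and bone scan) to 6 months from registration ± 2 weeks. Change sections 6.3.5 and 10.3 and Table 2 of section 6.4 together. In section 11.3.1, state that progression found in that window counts as a 6-month event in both the interim and the final Kaplan-Meier estimates. Add an interval-censored estimate of PFS and of the hazard rate as a sensitivity analysis, since re-timing one scan does not correct the hazard. A date counted from registration also covers patients who stop before external beam is complete.

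Cost: SAP wording and one follow-up visit's imaging, which moves between 3.3 weeks earlier and 3.7 weeks later under the scenarios above. No scan is added. The chest X-ray, examination and laboratory tests of that visit either move with it or are split from it.

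A nominal window replaces exact documentation dates at the landmark and so needs an explicit exception to section 11.3.5. The window spans 5.5 to 6.5 months, over which null PFS runs from exp(−0.3075 × 5.5) = 18% to exp(−0.3075 × 6.5) = 14%, but on average it returns the true value.

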11.0 STATISTICAL CONSIDERATIONS

11.1 OVERVIEW

This protocol will assess the proportion of clinical tumor responses, defined as progression-free survival at 6 months, and the toxicities associated with high-dose ^{153}Sm -EDTMP (MTD at 30 mCi/kg) after an initial lower dose of the agent along with external beam radiation therapy in patients with high-risk osteogenic sarcoma.

Primary objective: The primary objective of this study is to determine if the addition of external beam radiation therapy to infusional ^{153}Sm -EDTMP can delay the progression of target lesions. The primary endpoint is 6-month progression free survival (PFS). It is a combined effect of the entire treatment. To be evaluable, patients must meet all eligibility criteria, including signing a consent form, and have completed treatment according to protocol without major deviations. Patients who are enrolled but unevaluable will be replaced on the study. Only patients enrolled on Stratum 1 (i.e., with a diagnosis of osteosarcoma) will be evaluated for the Primary Objective.

Secondary objectives:

1. Describe the short and long-term toxicity profile of combined treatment with ^{153}Sm -EDTMP and external beam radiation therapy.
2. Estimate the local control rate. (Stratum 1 only)
3. Determine the overall survival (OS). (Stratum 1 only)
4. Describe the distribution of absorbed doses delivered to each targeted lesion and the distribution of equivalent uniform doses delivered to each patient.
5. Model the relationship between absorbed doses and time to progression.
6. Determine the correlation of hypoxic volume and maximum tumor/blood ratio obtained by [^{18}F]-MISO PET scanning with patient outcomes.

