9.2 CRITERIA FOR REMOVAL FROM STUDY

Patients will be removed from the study for patient or parent choice, or for excessive toxicity at the discretion of the principal investigators.

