11.2 STUDY DESIGN

This is a single-arm study with 2 strata: Stratum 1 for patients with osteosarcoma, and Stratum 2 for patients with other high risk solid tumors. Stratum 2 is exploratory in nature, and the goal of including these patients is to facilitate accomplishing secondary objectives related to toxicity and the feasibility of administering this treatment regimen to solid tumor patients. If possible, we will, however, use patients on Stratum 2 to estimate response rates of tumors other than osteosarcoma. For Stratum 1, 6-month PFS as the primary endpoint. The study will pre-specify target lesions for each patient in Stratum 1 that will be used to assess PFS, with the intention that every lesion radiographically evident at the time of enrollment will be a target lesion. Events will be the first disease progression at any of the target lesions or death from any cause. All patients treated on Stratum 1 will be included in the determination of PFS, regardless of treatment modification or discontinuation. The design will include interim analyses for futility if it seems unlikely that the treatment has sufficient activity. The historical PFS in 11 patients treated with ¹⁵³Sm-EDTMP similar to how we are proposing, but without the external beam component, was 15.8%. For this study of ¹⁵³Sm-EDTMP plus external beam radiation therapy, a 6-month PFS of 35% would be the lowest that would be considered acceptable, and PFS that is convincingly worse than this would be considered grounds for discontinuing further study. The non-parametric Kaplan-Meier estimate will be used to monitor the PFS function. After 8 patients have been enrolled, the design will include an interim analysis for futility that could halt the trial if it seems likely that this regimen does not have sufficient clinical activity. The study is designed to stop if we are 80% certain that the 6-month PFS is below 15%.

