11.3 STATISTICAL ANALYSIS PLAN

11.3.1 Estimate the PFS for subjects treated on Stratum 1.

Sample size: The primary measure of efficacy will be PFS at 6-months for Stratum 1 patients. In specific, the 6-month PFS for this treatment will be compared to a reference of 15.8% (hazard rate = 0.308/person-month i.e. median of 2.25 months). In patients with metastatic osteosarcoma a 6-month PFS of 35% would be considered promising, and is the benchmark for this study. Assuming exponential survival, 4 patients per year will be accrued for 5 years (20 total), one year of additional follow-up, and a one-sided 0.05 alpha level test, the sample size of 20 will have 82% power to detect a hazard ratio of 1.76.

Early stopping guideline for safety: The study will be monitored after every patient for non-hematologic grade 4 toxicities following initiation of external beam radiation therapy. This stopping rule for toxicity will hold enrollment if the posterior probability of risk being larger than 0.2 is 75% or higher. The prior for this toxicity monitoring rule is beta (1, 5). This distribution means that our prior guess at this type of grade 4 toxicity is 16.7%, and there is 95% probability that it is between 0.51% and 52.2%. The operating characteristics of the stopping rule are shown below and are based on 5000 simulations:

Toxicity stopping rule:

Study termination if:	2 AEs	3 AEs	4 AEs	5 AEs	6 AEs
And number of patients between:	2 - 3	4 - 7	8 - 12	13 - 16	17 - 20

Operating characteristics of stopping rule based on 5000 simulations:

True Toxicity Risk	Prob. Declare Treatment Too Toxic	Avg. Sample Size
0.05	1.0%	19.8
0.10	6.4%	19.2
0.15	17.1%	17.9
0.20	33.7%	16.2
0.25	54.0%	13.8
0.30	69.1%	12.0
0.35	82.9%	9.7
0.40	92.6%	7.9

Early stopping guideline for futility and simulations: Simulation is used to demonstrate the operating characteristics of the study for a sample size of 20. The study will be monitored for futility with a primary endpoint of 6-month PFS. The non-parametric Kaplan-Meier estimate will be used to estimate the PFS function at 6-months. After 8 patients have been enrolled, the design will include an interim analysis for futility that could halt the trial if it seems likely that the treatment does not have sufficient clinical activity.

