The sample size of 20 and the study design operating characteristics assume a 5 year accrual period with an additional follow-up of one year. The null 6-month PFS is 15.8%. We have designed the study to stop early only if the posterior probability of 6-month PFS being less than 0.15 is 80% or higher. Simulations were carried out with exponential survival and staggered patient entry. We assume on average 1 patient will enter the study every three months. Interim analyses begin once 8 patients have been entered on the study and occur after groups of 4 patients thereafter up to a maximum of 20 patients. The interim analysis estimates of 6-month PFS are based on analyses with an underlying Dirichlet process prior. We approximate the posterior distribution, which is actually a mixture of Beta distributions, the mixture depending on the amount of censoring, with a single Beta distribution. The parameters of this posterior Beta distribution are based on the number of failures and the effective sample size at 6-months, combined with the parameters of the prior.

The following table summarizes the operating characteristics of the futility stopping rule under various scenarios for the underlying exponential PFS, based on 5000 simulations. For futility monitoring we characterize the uncertainty of the 6-month PFS estimate with the prior: beta (1, 4). This implies that our prior guess at the 6-month PFS in this study is 20% and there is 90% certainty that the 6-month PFS is between 1.3% and 52.7%.

Table 2. Interim monitoring rule operating characteristics

6-month PFS	Prob Stop for Futility	Avg N	Estimated 6-mo PFS	lo 90% Post Int'l	hi 90% Post Int'l
0.10	0.60	14.2	0.07	0.0	0.20
0.15	0.39	16.2	0.12	0.0	0.30

0.20	0.23	17.7	0.18	0.0	0.35
0.25	0.12	18.7	0.23	0.0	0.40
0.30	0.07	19.2	0.29	0.0	0.45
0.35	0.04	19.6	0.34	0.15	0.50
0.40	0.02	19.8	0.40	0.20	0.60

Analysis for primary objective: Overall hazard rate estimates and 95% confidence intervals as well as Kaplan-Meier (KM) estimates will be used to summarize PFS over time. The 6-month PFS with 95% confidence interval will be reported.

11.3.2 Describe the toxicity profile of this regimen in the short and long-term.

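### Sections 11.1 and 11.2 give different rules on which treated Stratum 1 patients count; 11.2 is the more specific, but the plan never says that 11.1 governs replacement only, nor whom the planned 20 counts

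*Combined protocol and SAP*

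**What the plan says.** Section 11.1, in the paragraph that names 6-month PFS as the primary endpoint, sets two conditions. The first is eligibility: "To be evaluable, patients must meet all eligibility criteria, including signing a consent form". The second is that patients "have completed treatment according to protocol without major deviations. Patients who are enrolled but unevaluable will be replaced on the study". The same paragraph then says that only Stratum 1 patients, meaning those with osteosarcoma, are evaluated for the primary objective.

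Section 11.2 states the set for the endpoint itself: "All patients treated on Stratum 1 will be included in the determination of PFS, regardless of treatment modification or discontinuation". The title of 11.3.1 uses the same population: "Estimate the PFS for subjects treated on Stratum 1".

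Other relevant places:
- Section 11.3.5 starts the clock before treatment: "Progression-free survival is defined as time from registration to the first observation (documentation) of disease progression or death".
- Section 9.2 on stopping: "Patients will be removed from the study for patient or parent choice, or for excessive toxicity", the latter at the discretion of the principal investigators. Progression is not listed.
- Section 12.03 takes patients who never receive protocol therapy off protocol. It says nothing about those who start and do not finish.
- Section 11.3.1 gives power for 20 patients, ends the toxicity boundaries at 17 to 20 patients, and runs futility looks up to a maximum of 20. It does not say whether these are treated or evaluable patients.

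**The concern.** Evaluability in 11.1 appears within the primary objective and uses the language of analysis, so it can be read as defining who enters the primary result. A patient taken off for toxicity after starting treatment would then be dropped and replaced, while 11.2 counts that patient.

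The trial has one arm and compares 6-month PFS with a fixed 15.8%. No control group is exposed to the same selection. Because PFS starts at registration and completion comes later, a set limited to completers is chosen on events inside the follow-up period. If some of those left out progressed or died early, the estimate is too high.

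A second gap remains even if 11.1 is read only as a replacement rule. Treated patients who are replaced and still counted can take the analysed number above 20, and the plan does not say how the power statement and the monitoring rules then apply.

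**Working it through.** **1. The plan's own figure.** Inputs from 11.3.1: reference 6-month PFS 15.8%, target 35%, exponential PFS, 20 patients, one-sided 0.05.
- Null hazard = −ln(0.158)/6 = 0.3075 per month; target hazard = −ln(0.35)/6 = 0.1750; ratio 1.76.
- Exact exponential test with all 20 patients followed to an event: reject if 2 × 0.3075 × (sum of times) exceeds 55.76, the 95th percentile of chi-square with 40 degrees of freedom. Power = P(chi-square with 40 df > 55.76/1.76 = 31.7) = 82%.

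This agrees with the plan: "a one-sided 0.05 alpha level test, the sample size of 20 will have 82% power to detect a hazard ratio of 1.76". The sample-size arithmetic is not in question.

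**2. The two rules side by side** (Stratum 1, osteosarcoma)

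| Patient | 11.1 | 11.2 |
|---|---|---|
| Eligible, completed, no major deviation | Evaluable | Counted |
| Started, stopped early | Unevaluable, replaced | Counted |
| Completed with a major deviation | Unevaluable, replaced | Counted, as treated |
| Treated, later found to fail another entry criterion | Unevaluable, replaced | Counted, as treated |
| Registered, never treated | Unevaluable, replaced | Not counted |

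The rules differ in rows 2 to 4. In those rows 11.1 states replacement; it does not state removal from PFS.

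**3. Size if 11.1 were used as the analysis set.** The documents do not give the number of non-completers or how many of them fail early, so this is an illustration over an assumed range. Of 20 treated patients at the reference rate, 20 × 0.158 = 3.16 are expected to be progression-free at 6 months. If m of the 20 are early failures and are replaced by completers with the same outlook as the remaining patients, the expected estimate is 0.158/(1 − m/20):

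| m | Expected 6-month PFS | Shift |
|---|---|---|
| 0 | 15.8% | 0 |
| 1 | 0.158/0.95 = 16.6% | 0.8 points |
| 2 | 0.158/0.90 = 17.6% | 1.8 points |
| 4 | 0.158/0.80 = 19.8% | about 4 points |

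For scale, the reference and target differ by 35 − 15.8 = 19.2 points. The shifts for m = 2 and m = 4 are about 9% and 21% of that distance. Only early failures matter: if 4 patients are excluded for reasons unrelated to outcome, the expected value stays at 15.8%.

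**4. Size under 11.2.** No treated patient is removed, so the shift is zero.

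**The case against.** The strongest reply is that the plan largely settles the matter. Section 11.2 speaks directly about PFS, the title of 11.3.1 repeats its population, and the only consequence that 11.1 attaches to being unevaluable is replacement. The two rules can hold together: replace the patient for accrual, and still count them. This stands. It makes 11.2 the better reading, and replacing a treated patient who is still counted does not in itself select on outcome. It does not remove the need for a clarifying sentence, because 11.1 does not limit itself to accrual, and this reading is the one under which the number treated can pass 20.

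A reader might go further and infer that the primary analysis is restricted to completers and so is biased. The documents do not support that, since 11.2 says the opposite.

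A reader might also infer a large bias by supposing that every failure before the end of treatment is excluded. With completion assumed at 1 to 2 months after registration, the exponential model puts 26.5% to 45.9% of null failures before that point, and the expected estimate would be 0.158/(1 − 0.265) = 21.5% to 0.158/(1 − 0.459) = 29.2%. The documents give no length for the external beam course and point away from this extreme. Scheduled restaging comes one month after external beam ends (6.2, 10.2), life expectancy must exceed 8 weeks (5.1.5), and progression is not a removal criterion (9.2). If only 5% to 10% of those early failures were excluded, the result would be 16.0% to 16.6%.

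Nor can a definite inflation of the false-positive rate be claimed. The plan gives a significance level but names no test. For the primary result it commits to hazard estimates, Kaplan-Meier curves and an interval: "The 6-month PFS with 95% confidence interval will be reported".

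**Conclusion.** The point holds as an unreconciled definition of the primary set. Sections 11.1 and 11.2 treat the same patients differently; 11.2 is the more specific rule and introduces no selection, but no section ranks the two or says what the 20 counts. The bias is conditional. It is zero under 11.2. If 11.1 were used for analysis it would be upward to the extent that the excluded patients are early failures, about 2 to 4 percentage points on a true 15.8% if 2 to 4 of 20 are replaced for that reason. Those counts are assumed, not taken from the documents. The textual conflict is certain; any effect on the reported result is not. It should be corrected because the comparison is with a fixed reference and the correction is only wording.

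**What to change.** In 11.1, add text to this effect:

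*The primary PFS analysis set is all Stratum 1 patients (confirmed osteosarcoma) who receive any study treatment, analysed from registration regardless of treatment modification, discontinuation or protocol deviation, as in 11.2. The evaluability condition removes no treated patient from this analysis; it governs replacement only, and may define a supportive analysis. Any treated patient who is replaced is still counted in PFS.*

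Naming confirmed osteosarcoma keeps the set in line with 11.1's own definition of Stratum 1, so a patient later found to have another diagnosis is not carried in it. There is no need to forbid replacement of treated patients.

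In 11.3.1, state whether the 20 in the power, futility and toxicity rules counts treated patients. If it counts evaluable patients instead, say how the monitoring rules apply once more than 20 have been treated.

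The cost is a few sentences. The stated power for 20 stands if 20 means treated patients. The estimate may be slightly less favourable than one from completers alone.
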